5.1 Statistical Methods

5.1.1 Hypotheses and Statistical Methods for Primary Objective(s)

5.1.1.1 Hypotheses

Primary analyses will be performed on the Per-Protocol Analysis Set and on Full Analysis Set.

The objective is to demonstrate that the humoral response (in terms of seroconversion) of vYF (Group 1) is non-inferior to YF-VAX (Group 2) 28 days after a single dose in YF-naïve participants.

The percentages of participants with seroconversion 28 days after vaccination will be used to compare responses between Group 1 and Group 2 with the following hypotheses:

- H0 (Null hypothesis): $p(vYF) p(YF-VAX) \le -\delta$
- H1 (Alternative hypothesis): $p(vYF) p(YF-VAX) > -\delta$

Where δ the non-inferiority margin is set to 5%.

Where p(vYF) and p(YF-VAX) are the proportion of participants with seroconversion. Seroconversion is defined as a fourfold increase in NAb titers as compared to pre-vaccination value.

In the last version of the protocol (version 4 approved on 16^{th} February 2022), the D29 visit is to be performed with a time window of +3 days; a blood sample BL0003 has to be taken at the D29 visit.

However, the timing for the Phase II non-inferiority VYF02 study has been complicated by COVID epidemic waves and vaccination campaigns; when non-COVID work was resuming at Investigational sites, these studies were competing against other studies. As a direct consequence, the enrolments were delayed and longer than expected. Considering that the planned sample size

was likely to be not reached, the Applicant worked on a mitigation plan based on the number of evaluable subjects (derived from the attrition rate used for the statistical hypotheses) consisting of extending the time window of the D29 post-vaccination visit (initial defined as D29 + 3 days) with a proposal to extend up to D29 + 6 days, as the immune responses should not be impacted by this extension. The analyses with a revised time window for the D29 visit +6days will be presented as the primary analysis of the non-inferiority of the antibody response in terms of seroconversion rates 28 days after vaccine administration of one dose of vYF (administered on D01) compared to the antibody response after one dose of the YF-VAX control vaccine (administered on D01) in YF-naïve participants. If the primary objective is reached, in secondary objective, the originally planned analysis of the non-inferiority of the antibody response on D29 with a time window of +3 days will be presented too on the YF-naïve population only and completed with a descriptive analysis in terms of seroconversion, seroprotection, GMT and GMTR.

The non-inferiority will be demonstrated if the lower limit of the 2-sided 95% confidence interval (CI) of the difference between the 2 percentages is > -5%.

The CI of the difference in percentages will be computed using the Wilson score method without continuity correction as quoted by Newcombe (3) for seroconversion rates.

5.1.2 Hypotheses and Statistical Methods for Secondary Objective(s)

5.1.2.1 Hypotheses

No hypotheses will be tested. Descriptive statistics will be presented.

5.1.2.2 Statistical Methods

Immunogenicity:

Analyses will be performed on the Full Analysis Set

The immunogenicity parameters will be described per vaccine group. Immunogenicity analyses will be provided on participants by YF serostatus and by FV serostatus.

The following parameters will be analyzed:

- GMT for each vaccine group
- Seroconversion rates using previous timepoints as reference: number and percentage of participants in each vaccine group converted with neutralizing antibody titer 4-fold increase compared to the previous time point, at D11 compared to D01 (subset only), at D29 compared to D01, at M6 compared to D01, at Y1 compared to M6, at Y2 compared to Y1, at Y3 compared to Y2, at Y4 compared to Y3, at Y5 compared to Y4
- Within-group GMTR for each vaccine group post-vaccination injection, compared to D01 (D11/D01 [subset only], D29/D01, M6/D01 and yearly ratios: Y1/M6, Y2/Y1, Y3/Y2, Y4/Y3, Y5/Y4.

- Number and percentage of participants (seroprotection rates) in each vaccine group with antibody titer ≥ 10 (1/dil) at baseline (D01) and at D11 (subset only), D29, M6 and yearly from Y1 to Y5
- Distribution of titers against YF at each time point and corresponding RCDC

The 95% CIs will be calculated using:

- The normal approximate method for GMTs and GMTRs
- The exact binomial distribution for percentages (Clopper-Pearson's method, quoted by Newcombe)

Assuming that log10 transformation of the titers/ratios follows a normal distribution, first, the mean and 95% CI will be calculated on log10 (titers/ratios) using the usual calculation for normal distribution, then antilog transformations will be applied to the results of calculations, to compute GMTs/GMTRs and their 95% CIs.

Complementary immunogenicity analysis based on the planned analysis on D29 with a time window of +3 days will be performed on a sub-population of the Per-Protocol Analysis Set:

- Non-inferiority analysis of the antibody response on D29
- GMT for each vaccine group
- Seroconversion rates: number and percentage of participants in each vaccine group converted with neutralizing antibody titer 4-fold increase compared to the previous time point, at D29 compared to D01
- Within-group GMTR for each vaccine group D29 post-vaccination injection, compared to D01
- Number and percentage of participants (seroprotection rates) in each vaccine group with antibody titer ≥ 10 (1/dil) at baseline (D01) and at D29

Safety:

Safety results will be described per vaccine groups on the SafAS. The main parameters for the safety endpoints will be described by 95% CIs of point estimates, calculated using the exact binomial distribution from Clopper-Pearson's method quoted by Newcombe (2) for proportions.

Biological safety results (biochemistry and hematology for subset of subjects only):

Hematology and biochemistry out-of-range test results will be summarized at D01 and D11 after vaccination for participants in the subset. The hematology and biochemistry laboratory parameters at baseline and Day 11 visit will also be summarized in the form of a table showing the number of subjects with values over time according to the intensity grading scales. Shift tables for hematology and biochemistry laboratory parameters with reference ranges will present the number (%) of subjects with laboratory results with Grade 1, Grade 2 and Grade 3 (see Table 4.1) at Day 11 visit relative to baseline by vaccine group including total values. Parameters to be presented will be biochemistry (ALT, AST, CPK, alkaline phosphatase, bilirubin, creatinine, CRP), and hematology (RBC count, hemoglobin, hematocrit, MCV, platelets count, WBC count,

and quantitative differential count [neutrophils, lymphocytes, monocytes, eosinophils, basophiles]) on Day 01 visit and Day 11 visit.

Subjects with abnormal intensity grade will be presented for the hematology and biochemistry listings. The results will be displayed in their original units.

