A subset of 90 participants (60 participants in Group 1 and 30 participants in Group 2) enrolled in a limited number of sites will provide an additional post-vaccination blood sample at D11 to assess the immune response elicited by both vaccines, and biological safety parameters on D01 and D11.

Since participants will not be screened for a history of prior FV infection or vaccination, it is likely that some participants have evidence for past FV infection or vaccination by the assessment

of FV serostatus at baseline. Given the small numbers of FV-experienced individuals expected in USA settings, the absence of any safety concern for FV-seropositive individuals receiving the investigational vaccination and the infeasibility of performing, offsite, virus neutralization titers in the course of participant recruitment, the assessment at baseline of FV serostatus will not be used as a criterion for study eligibility. FV- or YF-seropositive participants will therefore not be excluded from the study and seroconversion will be evaluated in this population as a secondary objective.

In addition, for the purpose of assessing the impact on immunogenicity, neutralizing antibody titers against a panel of epidemiologically important and immunologically relevant FVs (such as Zika virus, or dengue serotypes 1-4 viruses) will be measured on baseline sera, prior to vaccination, for the analysis of the immune response based on serostatus at baseline.

As a secondary objective for this Phase II study, safety of the new vYF vaccine candidate will be also described.

As a consequence, the total enrolled cohort is 570 participants (380 participants in Group 1 [vYF] and 190 participants in Group 2 [YF-VAX]).

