8.1.2 Immunogenicity Assessments

The primary objective of this study is to demonstrate the non-inferiority of the antibody response in terms of seroconversion rates 28 days after vaccine administration of one dose of vYF administered on D01 compared to the antibody response after one dose of the YF-VAX (control vaccine) administered on D01 in a YF-naïve population. YF-naïve participants (or negative) at baseline correspond to participants with no detectable YF Ab titers before vaccination. YF seronegative at baseline is defined as a titer < LLOQ for the assay (any participant with a baseline

^{*3} more mL of blood sample may be collected at V1 in case a HIV test needs to be performed

titer \geq LLOQ will be eliminated from the primary analysis [Per-protocol analysis]). LLOQ determined as 10 (1/dil), also defined the threshold of protection.

Seroconversion is defined as a 4-fold increase in NAb titers, as compared to the pre-vaccination value, while seroprotection is defined as NAb titers ≥ threshold of 10 (1/dil).

The secondary objectives are to describe the immune response to YF in both vaccine groups using YF MN assays before (D01) and after vYF or YF-VAX administration, by determining seroconversion and seroprotection as well as GMT and GMTR in all participants at several timepoints (D11 in a subset only, D29, M6, and yearly from Y1 to Y5).

All secondary objectives will be analyzed depending on the flavivirus status at baseline (YF-naïve and immune, dengue serotypes 1-4 naïve and immune, Zika-naïve and immune, and FV-naïve and immune).

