	The corresponding parameters are seroconversion rate, seroprotection rate, GMT, and GMTR.	
	Seroprotection is defined as NAb titers \geq threshold of 10 (1/dil).	
	Data will be analyzed depending on FV immune status at baseline (YF-naïve and immune, FV-naïve and immune, dengue serotypes 1-4 naïve and immune, Zika- naïve and immune).	
• To describe the immune response to YF in both vaccine groups using YF MN assays between D01 and D29 using the D29 +3 days time window in YF-naïve participants.	 Seroconversion rates at D29 Seroprotection rates at baseline (D01) and at D29 Geometric means of the individual titers ratios for D29/D01 	
Safety		See section 8.2 of the protocol

Objectives			Endpoints	Assessment		
•	To describe the safety profile of vYF vaccine in comparison to the safety profile of the control YF- VAX To describe the safety of	•	Presence, nature (Medical Dictionary for Regulatory Activities [MedDRA] preferred term), duration, intensity and relationship to vaccination of any unsolicited systemic adverse events (AEs)			
	vaccination in all participants up to 28 days after vaccination	•	reported in the 30 minutes after vaccination Presence, time to onset, number of			
•	To describe all serious adverse events (SAEs) up to 6-month follow-up		days of presence, and intensity of solicited (pre-listed in the participant's diary and electronic case report form [eCRF]) injection			
•	To describe related SAEs and all deaths from D01 to		site reactions up to 7 days after vaccination			
•	To describe all AESIs up to 6-month after vaccination;	•	Presence, time to onset, number of days of presence, and intensity of solicited systemic reactions up to 14 days after vaccination			
•	To describe the biosafety profile of vYF in comparison to the biosafety profile of the control YF-VAX in a subset only	•	Presence, nature (MedDRA preferred term), time to onset, duration, intensity, and relationship to vaccination (for systemic AEs only) of unsolicited (spontaneously reported) AEs up to 28 days after vaccination and AESIs up to 6- months after vaccination			
		•	Presence of any serious adverse events (SAEs) including serious AESIs, up to 6-month after vaccination			
		•	Presence of related SAEs and all deaths from D01 to 5 years after vaccination			
		•	Hematology and biochemistry out- of-range test results at D01 and D11 in a subset only ⁺			
Ex	ploratory					

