4.2.1.4 Baseline Serostatus

The baseline serostatus (eg, YF naïve participants and YF immune, Dengue naïve and Dengue immune, Zika naïve and Zika immune) is defined as the presence of antibodies (Abs) in the baseline blood sample collected at Visit 1 (V01) in the present study from all participants.

YF naïve participants are participants with baseline YF NAb value below the threshold for protection [< 10 (1/dil)]. If the NAb value is \geq 10 (1/dil) then the YF immune indicator will be "Immune". Otherwise the baseline YF serostatus will be classified as "Undetermined".

The serostatus of dengue is computed based on values of dengue NAb titers against each of the four serotypes at V01. If the NAb value is positive (≥ 10 [1/dil]) for any serotype, then the dengue immune indicator will be "Immune". Else if the NAb value is not positive (< 10 [1/dil) and non-missing for all four serotypes (ie, all of the titers planned to be measured at baseline must be available, and valid [not coded "NR" in the serology database] then the dengue immune indicator will be "Naive". Otherwise the baseline serostatus will be classified as "Undetermined".

Zika serostatus will be determined using a Zika microneutralization test for serum samples obtained at baseline. Zika immune samples were defined as having a Zika antibody titer of \geq 100 (1/dil) (1). If the NAb value is not positive (< 100 [1/dil]) and non-missing (ie, the titers planned to be measured at baseline must be available, and valid [not coded "NR" in the serology database]), then the Zika immune indicator will be "Naive". Otherwise the baseline Zika serostatus will be classified as "Undetermined".

Flavivirus immune participants at baseline are defined as participants either immune to YF or immune to Dengue or immune to Zika at baseline. Flavivirus naive participants at baseline are defined as participants naïve to YF and naive to Dengue and naive to Zika at baseline. Otherwise the baseline Flavivirus serostatus will be classified as "Undetermined".

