	Ratio V08 (V01+3Y)/ V07 (V01+2Y)	###	###.#	(###.#; ###.#)	###	###.#	(###.#; ###.#)	
	Ratio V09 (V01+4Y)/ V08 (V01+3Y)	###	###.#	(###.#; ###.#)	###	###.#	(###.#; ###.#)	
	Ratio V10 (V01+5Y)/ V09 (V01+4Y)	###	###.#	(###.#; ###.#)	###	###.#	(###.#; ###.#)	
Naïve								

Table 7.3: Summary of geometric means of titers and geometric means of individual titer ratios of antibody against YF virus by FV status at baseline - Microneutralization assays - Full Analysis Set

* Subset only

M: Number of participant s available for the endpoint

Flavivirus status: Immune for participants with quantified (\geq LLOQ) neutralizing Abs against YF, and/or against at least one dengue serotype, and/or Zika in the baseline sample; naive for participants without quantified (\leq LLOQ) neutralizing Abs against YF, with no Ab quantified against any of the four dengue serotypes and Zika in the baseline sample.

Table 7.4: Summary of percentages of participants achieving seroconversion after one dose YF vaccination by YF status at baseline - Microneutralization assays - Full Analysis Set

YF status Time point		vYFv (N=xxx)			YF-VAX (N=xxx)			
		Seroconversion rate			Seroconversion rate			
		n/M	(%)	95% CI	n/M	(%)	95% CI	
Immune	V02 (V01+10d)/ V01 (Pre-inj)	###/###	##.#	(##.#; ##.#)	###/###	##.#	(##.#; ##.#)	
	V04 (V01+28d)/ V01 (Pre-inj)	###/###	##.#	(##.#; ##.#)	###/###	##.#	(##.#; ##.#)	
	V05 (V01+6M)/ V01 (Pre-inj)	###/###	##.#	(##.#; ##.#)	###/###	##.#	(##.#; ##.#)	
	V06 (V01+1Y)/ V05 (V01+6M)	###/###	##.#	(##.#; ##.#)	###/###	##.#	(##.#; ##.#)	
	V07 (V01+2Y)/ V06 (V01+1Y)	###/###	##.#	(##.#; ##.#)	###/###	##.#	(##.#; ##.#)	
	V08 (V01+3Y)/ V07 (V01+2Y)	###/###	##.#	(##.#; ##.#)	###/###	##.#	(##.#; ##.#)	
	V09 (V01+4Y)/ V08 (V01+3Y)	###/###	##.#	(##.#; ##.#)	###/###	##.#	(##.#; ##.#)	
	V10 (V01+5Y)/ V09 (V01+4Y)	###/###	##.#	(##.#; ##.#)	###/###	##.#	(##.#; ##.#)	
Naive	•••						. , ,	

n: Number of participant s who achieve a yellow fever vaccination seroconversion.

M: Number of participant s with available data for the endpoint.

Seroconversion: For a participant with a fourfold increase in NAb titers as compared to the previous timepoint value

YF status: Immune for participants with quantified (\geq LLOQ) neutralizing Abs against YF; naive for participants without quantified (\leq LLOQ) neutralizing Abs against YF in the baseline sample.

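### SAP 5.1.2.2 and the main-output shells omit the dengue and Zika strata listed in SAP 4.1, and their FV-immune rows mix in YF-immune participants

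*SAP*

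**What the plan says.** Protocol 4.2 gives the reason for the baseline serology: "for the purpose of assessing the impact on immunogenicity, neutralizing antibody titers against a panel of epidemiologically important and immunologically relevant FVs" are measured before vaccination, so that the response can be analysed by serostatus.

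Protocol 8.1.2 states that "All secondary objectives will be analyzed depending on the flavivirus status at baseline" and names YF, dengue 1-4, Zika and FV, each naive and immune. SAP 4.1 repeats this: "Data will be analyzed depending on FV immune status at baseline (YF-naïve and immune, FV-naïve and immune, dengue serotypes 1-4 naïve and immune", followed by Zika.

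SAP 4.2.1.4 derives each indicator. For dengue, "The serostatus of dengue is computed based on values of dengue NAb titers against each of the four serotypes at V01". A separate rule covers Zika. The pooled category is then a union: "Flavivirus immune participants at baseline are defined as participants either immune to YF or immune to Dengue or immune to Zika at baseline".

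The methods section, SAP 5.1.2.2, is shorter: "Immunogenicity analyses will be provided on participants by YF serostatus and by FV serostatus". Protocol 9.4.2 contains the same sentence. The shells in SAP section 7 follow it. Tables 7.2, 7.4 and 7.6 and Figures 7.1-7.2 are by YF status; Tables 7.3, 7.5 and 7.7 and Figures 7.3-7.4 are by FV status. The FV table footnotes define immune as having quantified "neutralizing Abs against YF, and/or against at least one dengue serotype, and/or Zika in the baseline sample". The only other dengue or Zika output in the SAP is the baseline GMT per vaccine group in 5.1.3. Section 7 describes itself as covering main outputs and places the full shells in another document, which was not available.

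**The concern.** Two problems meet here. First, the section that tells the programmer what to run lists fewer strata than the section that lists the endpoints, and the SAP does not say which governs.

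Second, the pooled FV split that remains does not isolate what Protocol 4.2 wants to know. An FV-immune participant may be YF-naive with dengue or Zika antibody, which is the group of interest. The participant may instead already carry YF antibody. The second kind needs a 4-fold rise from a measured titer of at least 10, is seroprotected at baseline by definition, and can be expected to have a lower titer ratio. A lower seroconversion rate or GMTR in the FV-immune rows than in the FV-naive rows could therefore come from existing YF antibody and be taken for interference by other flaviviruses.

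**Working it through.** The plan states no figure that bears on this point, so there is none to reproduce.

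**1. Strata, side by side**

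| Place | YF | FV pooled | Dengue | Zika |
|---|---|---|---|---|
| Protocol 8.1.2 | yes | yes | yes | yes |
| SAP 4.1 | yes | yes | yes | yes |
| SAP 4.2.1.4 (derivation) | yes | yes | yes | yes |
| Protocol 9.4.2 | yes | yes | no | no |
| SAP 5.1.2.2 | yes | yes | no | no |
| SAP Tables 7.2-7.7, Figures 7.1-7.4 | yes | yes | no | no |

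**2. Baseline seroprotection in the FV-immune row.** Under SAP 4.2.1.4, YF-immune means a titer of at least 10 and YF-naive a titer below 10. Seroprotection uses the same cut at 10. Among participants with a determined YF status, the baseline seroprotection rate in the FV-immune row of Table 7.7 therefore equals the YF-immune share of that row. This needs no assumption, and the rate says nothing about dengue or Zika.

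**3. Seroconversion at D29.** Let y be the YF-immune share of the FV-immune row, f the seroconversion rate in YF-immune participants, and g the rate in YF-naive participants who are dengue- or Zika-immune. Then:

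- row rate = y·f + (1−y)·g
- shortfall against g = y·(g−f)

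The documents give none of the three. Assume g = 0.98 (no interference) and f = 0.30 to 0.70:

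| y | Row rate | Shortfall |
|---|---|---|
| 5% | 94.6% to 96.6% | 0.05 × 0.68 = 3.4 down to 0.05 × 0.28 = 1.4 points |
| 25% | 81% to 91% | 0.25 × 0.68 = 17 down to 0.25 × 0.28 = 7 points |

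With g = 0.95 and f = 0.10 to 0.50 instead, y = 25% gives 73.7% to 83.7%, a shortfall of 21.3 to 11.3 points. The size therefore depends on the assumed rates as well as the share.

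**4. GMTR.** Assume a GMTR of 100 in YF-naive and 3 in YF-immune participants. The row shows 3^y × 100^(1−y), which is 84 at y = 5% and 42 at y = 25%.

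**5. What subtraction recovers.** FV-immune is the union of YF-, dengue- and Zika-immune. Removing the YF-immune leaves those who are dengue- or Zika-immune but not YF-immune. FV-immune n/M in Table 7.5 minus YF-immune n/M in Table 7.4 gives that group's seroconversion count. Tables 7.7 and 7.6 do the same for seroprotection, and sums of log titers subtract in the same way, up to rounding. Two conditions apply. No one may have undetermined YF status, and FV-immune must have one settled meaning. The second is open: SAP 4.2.1.4 sets Zika-immune at 100 or more, whereas the shell footnotes use the LLOQ, which Protocol 8.1.2.2 gives as 10 for Zika.

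**6. What subtraction cannot recover.** Suppose dengue-only participants seroconvert in 10/10 and Zika-only in 5/10, or the reverse. Both give 15/20 in the remainder, so the YF and FV tables are identical. Dengue cannot be separated from Zika.

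**7. Precision of the added strata.** SAP 5.5 projects 304 and 152 evaluable participants. Assuming 2%, 5% or 10% fall in such a stratum (no prevalence is given), it holds about 6, 15 or 30 vYF and 3, 8 or 15 YF-VAX participants. If all n seroconvert, the Clopper-Pearson 95% lower bound is 0.025^(1/n): 29% at n = 3, 78% at n = 15 and 88% at n = 30.

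**The case against.** The strata are still in the SAP. Section 4.1 lists them and 4.2.1.4 derives them, so FV serostatus in 5.1.2.2 may be shorthand for the whole set. The short sentence is inherited from Protocol 9.4.2, and the full shells may contain the missing rows. A reader might infer that the sponsor abandoned the dengue and Zika analyses. The documents do not support that; they show an inconsistency. It still needs resolving, because 5.1.2.2 is the instruction to the programmer and the SAP is meant to be the more detailed text.

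The shell footnotes disclose that YF antibody counts towards FV-immune. Randomization means YF-immune participants are expected in similar proportions in both arms, so the vaccine comparison within the row is not biased by its make-up. Both points stand. However, judging the impact of serostatus means comparing immune with naive rows, and that comparison carries the mixing.

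Exclusions E03 and E06 remove known FV vaccination (including YF) and known FV infection, and Protocol 4.2 expects few FV-experienced participants. This argues against assuming a large YF-immune share. It does not fix the share, because E06 also removes people with known dengue or Zika infection.

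Finally, neither document promises a dengue or Zika split within YF-naive participants. That part is a recommendation, and the small strata limit what it can show.

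**Conclusion.** The point holds as an inconsistency in a secondary, descriptive analysis, together with a stratum definition that blurs its purpose. The outputs specified in 5.1.2.2 and the main shells do not directly show the effect of dengue or Zika immunity on the YF response, and they cannot separate the two. Only the baseline seroprotection result is free of assumptions. The shortfalls of about 1-3 points at a 5% share and 7-17 points at 25% rest on assumed rates of 98% and 30-70%.

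A reader might go further and conclude that the effect of heterologous immunity cannot be read at all. That is too strong, since subtraction rebuilds the combined dengue-or-Zika group under the stated conditions. A reader might also picture a distortion of several tens of points. That requires the YF-immune to be half or more of the stratum, and no document gives such a share. The primary non-inferiority analysis in YF-naive participants is unaffected.

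**What to change.** In SAP 5.1.2.2, and in Tables 7.3, 7.5 and 7.7 and Figures 7.3-7.4:

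1. Present the flavivirus split within YF-naive participants: dengue- and/or Zika-immune versus naive to both.
2. Add the dengue naive/immune and Zika naive/immune rows listed in SAP 4.1. If the full shells already hold them, say so in 5.1.2.2.
3. Keep the pooled FV-immune row as supplementary, with one definition of FV-immune in both the text and the footnotes.

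The cost is SAP wording and a subset flag in existing table programs, with no new samples or assays. The downside is small strata with wide intervals, so the rows should be read as descriptive only.
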